## **5.0 Power and Precision**

**5.1 Sample Size.** We expect to recruit 20,000 participants. Conservatively assuming 10% of them will not be evaluable, we expect to have data on 18,000 patients. It is estimated that 5% of the patients will be ineligible for aspirin,

2% will be ineligible for rivaroxaban and 1% will be ineligible for Warfarin. It is also estimated (based on the first 6 months of data) that 2.5% of those assigned to aspirin will not be treated with aspirin, 6.4% of those assigned to warfarin will not be treated with warfarin, and 13.6% of those assigned to rivaroxaban will not be treated with rivaroxaban. These patients will be excluded from the primary analysis. Therefore, with a total sample of approximately 20,000, we project that there will be 7239, 7223, and 5389 patients assigned to and treated with aspirin, Rivaroxaban, and Warfarin groups, respectively. We expect to have six-month outcome data on the vast majority of the patients, so we based our precision and power calculations on a binary outcome.

**5.2 Precision of Estimates.** The primary endpoint is a composite consisting of the occurrence of death from any cause and clinically evident PE or DVT. For an observed endpoint that occurs 1.1% of the time, considering the cross-over rates and conservatively assuming that 10% of those randomized will not have surgery or will be lost to follow-up, the margin of error of our estimates of risk will be 0.27%, 0.30%, and 0.35% for aspirin, rivaroxaban, and warfarin. Clinically significant bleeding is expected to occur in 0.5-1% of patients on aspirin, 4-5% of patients on rivaroxaban, and 1-2% of patients on warfarin. Given those percentages, the margin of error for estimates of bleeding risk will be 0.22%, 0.61%, and 0.41%, respectively.

**5.3 Power to confirm non-inferiority.** The adoption of a non-inferiority methodology for this trial was predicated on establishing the non-inferiority of aspirin, as compared to either warfarin or rivaroxaban, in preventing death and thromboembolic disease with the assumption that aspirin would very likely result in fewer bleeding complications than either of these two agents. The statistical test of non-inferiority will be based on only those who were medically or logistically eligible for randomization to either of the two groups being compared. Table 1 shows the power to detect non-inferiority for the comparison of aspirin to warfarin with no additional patients randomized to warfarin.

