**Table 1. Numbers of patients and resulting power and precision in comparing aspirin to warfarin.**

	Aspirin	Warfarin
Number Randomized as of May 1, 2023	5132	5389
Number Eligible for both treatments (either medically or due to logistics)	4703	4698
Projected number who took the assigned treatment 	4402	3688
Projected number who will have complete follow-up 	3962	3319
Projected width of the 95% CI for the difference in risk of primary outcome	0.96 percentage pts	
Power to obtain evidence of non-inferiority based on 0.69% margin of inferiority	80.3%	
Margin of inferiority detectable with 80% power	0.69 percentage pts	

Based on a crossover rate of 21.5% and 6.4% for Warfarin and Aspirin, respectively.

Assuming that 90% of those randomized have surgery, do not withdraw, and have 6-month follow-up information.

**Recruitment and randomization.** To achieve the total of approximately 18,000 evaluable patients we will recruit approximately 20,000 to accommodate the possibility of 10% loss to follow-up. We will randomize patients with equal probabilities to each of the three regimens using a web-based program provided by Statix. Those sites that are on the restricted randomization plan due to structural barriers will randomize patients using a 1:1 randomization scheme. Following removal of warfarin from the protocol in June 2023, all sites will randomize patients using a 1:1 scheme to either aspirin or rivaroxaban. The web application is available 24/7, password protected, and maintains an audit trail of transactions with time stamp login for users. There will be a separate randomization schedule for each clinical site, stratified according to operation (hip or knee) to ensure balanced intervention groups with respect to site and operation. Within each stratum, assignments will be randomly permuted within repeating blocks of varying size.

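### Section 5.1 labels as treated what appear to be numbers randomised, and its counts and crossover rates do not agree with Table 1 or with the margins of error in 5.2

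*Protocol*

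**What the plan says.** The passages are in the Protocol, Section 3.1.3 (Data Analysis), part 5.0 (Power and Precision).

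- **5.1, recruitment and attrition.** Recruitment is 20,000, with 18,000 expected to be evaluable after a 10% loss. From the first six months of data, "2.5% of those assigned to aspirin will not be treated with aspirin, 6.4% of those assigned to warfarin will not be treated with warfarin"; the corresponding figure for rivaroxaban is 13.6%. All such patients are to be left out of the primary analysis.
- **5.1, conclusion.** As a consequence, "we project that there will be 7239, 7223, and 5389 patients assigned to and treated with aspirin, Rivaroxaban, and Warfarin groups, respectively".
- **5.2.** For an endpoint occurring 1.1% of the time, allowing for crossover and a 10% loss, "the margin of error of our estimates of risk will be 0.27%, 0.30%, and 0.35% for aspirin, rivaroxaban, and warfarin".
- **Table 1 (aspirin versus warfarin).** The row "Number Randomized as of May 1, 2023" shows 5132 for aspirin and 5389 for warfarin. Of these, 4703 and 4698 are eligible for both drugs, 4402 and 3688 are projected to have taken the assigned drug, and 3962 and 3319 to have complete follow-up. Footnote 1 reads: "Based on a crossover rate of 21.5% and 6.4% for Warfarin and Aspirin, respectively".
- **Recruitment and randomization.** "To achieve the total of approximately 18,000 evaluable patients we will recruit approximately 20,000".

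**The concern.** The sentence in 5.1 presents its three counts as what remains after crossovers are removed, yet together they use up almost the whole recruitment target. The warfarin count also reappears in Table 1 under a different label.

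This matters because the primary analysis is per-protocol, so the number treated as assigned is the number that counts. Aspirin versus rivaroxaban is the only comparison still enrolling, and its non-inferiority statistic is the one written out in Section 1.2. Section 5.1 is the only place that prints per-arm counts for it, since Table 1 has no rivaroxaban column. If those counts are wrong, and the margins in 5.2 rest on attrition that 5.1 does not state, a reader cannot recover the planned size of the primary analysis set.

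**Working it through.** **Inputs.** Counts and crossover rates from 5.1; the 1.1% event rate, 10% loss and printed margins from 5.2; counts, crossover rates and 90% retention from Table 1; the 0.69-point margin from Section 1.2 and Table 1.

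**1. Table 1 reproduces.**
- Took assigned drug: 4703 × 0.936 = 4402; 4698 × 0.785 = 3688.
- Followed up: × 0.90 gives 3962 and 3319.
- SE of the difference = √[0.011 × 0.989 × (1/3962 + 1/3319)] = 0.2454 points. CI width = 2 × 1.96 × 0.2454 = 0.96 points.
- Power = Φ(0.69/0.2454 − 1.96) = 80.3%, as printed, at one-sided 0.025.

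Table 1 is therefore internally sound.

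**2. The 5.1 counts cannot be treated counts.**
- Sum: 7239 + 7223 + 5389 = 19,851.
- Randomised patients needed if these were treated: 7239/0.975 + 7223/0.864 + 5389/0.936 = 7425 + 8360 + 5757 = 21,542, which exceeds 20,000.
- As randomised counts they fit. 5389 equals Table 1's randomised warfarin count, with no more warfarin patients to come. Splitting the rest equally gives (20,000 − 5389)/2 = 7306 per arm, within about 1% of 7239 and 7223.

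**3. The crossover rates conflict.**

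| | 5.1 | Table 1 |
|---|---|---|
| Aspirin | 2.5% | 6.4% |
| Warfarin | 6.4% | 21.5% |
| Rivaroxaban | 13.6% | not given |

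**4. The 5.2 margins against 5.1.** Margin = 1.96 × √(0.011 × 0.989/n).

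| | n = 5.1 count × (1 − crossover) × 0.90 | Margin | Printed |
|---|---|---|---|
| Aspirin | 7239 × 0.975 × 0.90 = 6352 | 0.26% | 0.27% |
| Rivaroxaban | 7223 × 0.864 × 0.90 = 5617 | 0.27% | 0.30% |
| Warfarin | 5389 × 0.936 × 0.90 = 4540 | 0.30% | 0.35% |

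With no attrition the 5.1 counts would give 0.24%, 0.24% and 0.28%.

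**5. The 5.2 margins against Table 1.**
- Warfarin: n = 3319 gives 0.355%, in line with the printed 0.35%.
- Aspirin: 7239 × (4703/5132) × 0.936 × 0.90 = 5588 gives 0.27%, as printed.
- Rivaroxaban: applying Table 1's eligibility fractions to the 13.6% rate still falls short of 0.30%. With 4703/5132, n = 5147 and the margin is 0.285%; with 4698/5389, n = 4896 and the margin is 0.292%.

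**6. Size of the overstatement.** Inverting the printed margins, n = 1.96² × 0.011 × 0.989/margin² gives 5733, 4643 and 3412 followed up. Dividing by 0.90 gives about 6370, 5159 and 3791 treated.

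| Stated count compared with | Aspirin | Rivaroxaban | Warfarin |
|---|---|---|---|
| Treated, 5.1's rates (7058 / 6241 / 5044) | 3% | 16% | 7% |
| Treated, implied by 5.2 (6370 / 5159 / 3791) | 14% | 40% | 42% |
| Followed up, implied by 5.2 (5733 / 4643 / 3412) | 26% | 56% | 58% |

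**7. Power, aspirin versus rivaroxaban** (1.1% in both arms, margin 0.69 points, one-sided 0.025):
- 7239 and 7223: SE 0.1735, power 97.8%.
- 6352 and 5617: SE 0.1910, power 95.1%.
- 5733 and 4643: SE 0.2059, power 91.8%. At the lower rounding limits of the margins (5526 and 4492): SE 0.2095, power 90.9%.

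**The case against.** The strongest reply is that this is one mislabelled sentence and no result depends on it. Table 1 stands on its own inputs. Section 5.2 did not use the 5.1 counts as treated numbers, because its margins would then be smaller. The 18,000 figure is defined as recruitment less 10% and is never called the per-protocol set. All of this stands, and it limits the severity.

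Four stronger readings might be inferred but are not supported.

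- **That all three counts contradict Table 1.** Only the warfarin count does. Table 1's aspirin column is a May 2023 subset and there is no rivaroxaban column. Even the 3688 for warfarin is restricted to patients eligible for both drugs. That 7239 and 7223 are randomised counts is a strong inference, not something the Protocol states.
- **That the 5.2 margins have no basis.** Warfarin agrees with Table 1, and aspirin agrees once Table 1's eligibility and crossover steps are applied. Only rivaroxaban is unexplained by the rate printed for it.
- **That the treated set is overstated by 22–63% per arm.** That range sets treated counts against sizes that also carry the 10% loss, at the rounding extremes of the printed margins.
- **That the trial is underpowered.** Step 7 of the working shows otherwise on its stated assumptions.

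**Conclusion.** The point holds as an error in the stated figures. Section 5.1 announces an exclusion that its counts do not reflect. The warfarin count is shown to be mislabelled by direct comparison with Table 1; the other two very probably are as well. The crossover rates in 5.1 and Table 1 are unreconciled, and the rivaroxaban margin in 5.2 cannot be traced to the rivaroxaban rate the Protocol prints.

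The size depends on the benchmark. Like for like with treated patients, the excess runs from 3/16/7% on 5.1's own rates to about 14/40/42% on what 5.2 implies (aspirin/rivaroxaban/warfarin). The 26/56/58% figures compare the stated counts with followed-up patients, which is a different quantity. The 5.2-based values assume a Wald margin at 1.1% and depend on rounding of the printed margins.

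The conclusions the trial can reach are not threatened: power for aspirin versus rivaroxaban stays at about 91% or more under equal 1.1% risks and one-sided 0.025. This should be fixed, but it is not critical.

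**What to change.** 1. Confirm what 7239 and 7223 represent and, once confirmed, relabel all three counts in 5.1 as projected numbers randomised.
2. Use one current set of crossover rates for all three arms in 5.1, 5.2 and Table 1, including an updated rivaroxaban rate in place of the first-six-months figure.
3. Restate eligible, treated and followed-up counts per arm, and recompute the 5.2 margins from them.
4. Give the same counts and the power for aspirin versus rivaroxaban, in the form Table 1 uses for aspirin versus warfarin.
5. State that the 18,000 evaluable patients are counted before the per-protocol exclusions.

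The cost is rewording and recalculation. The stated sizes become less favourable; no extra patients are needed.

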**Table 1. Numbers of patients and resulting power and precision in comparing aspirin to warfarin.**

	Aspirin	Warfarin
Number Randomized as of May 1, 2023	5132	5389
Number Eligible for both treatments (either medically or due to logistics)	4703	4698
Projected number who took the assigned treatment 	4402	3688
Projected number who will have complete follow-up 	3962	3319
Projected width of the 95% CI for the difference in risk of primary outcome	0.96 percentage pts	
Power to obtain evidence of non-inferiority based on 0.69% margin of inferiority	80.3%	
Margin of inferiority detectable with 80% power	0.69 percentage pts	

Based on a crossover rate of 21.5% and 6.4% for Warfarin and Aspirin, respectively.

Assuming that 90% of those randomized have surgery, do not withdraw, and have 6-month follow-up information.

**Recruitment and randomization.** To achieve the total of approximately 18,000 evaluable patients we will recruit approximately 20,000 to accommodate the possibility of 10% loss to follow-up. We will randomize patients with equal probabilities to each of the three regimens using a web-based program provided by Statix. Those sites that are on the restricted randomization plan due to structural barriers will randomize patients using a 1:1 randomization scheme. Following removal of warfarin from the protocol in June 2023, all sites will randomize patients using a 1:1 scheme to either aspirin or rivaroxaban. The web application is available 24/7, password protected, and maintains an audit trail of transactions with time stamp login for users. There will be a separate randomization schedule for each clinical site, stratified according to operation (hip or knee) to ensure balanced intervention groups with respect to site and operation. Within each stratum, assignments will be randomly permuted within repeating blocks of varying size.

### Missing Data

A high retention rate of enrolled participants is critical to the internal and external validity of a randomized clinical trial. Patients who are more difficult to locate or are less cooperative in follow-up participation generally have lower social and residential stability, poorer treatment outcomes, and are more likely to experience financial, marital

status, and occupational changes. Many of these same factors are also well known to contribute to differences in health outcomes, health disparities, and healthcare utilization differences. To minimize non-response and loss to follow-up bias, we will rely on independent established third party data collectors who will devote considerable levels of charted effort to follow-up data collection. This approach to centralized data collection will ensure serial efforts to obtain follow-up of research subjects through mail, telephone, electronic communication, and web-enabled online surveys. It will incorporate a 1-800 message, fax and e-mail options for participant convenience, and use postage-paid reply mail service, address forwarding, and multiple efforts in multiple formats to locate patients whose addresses, phone numbers or e-mail become insufficient. Participants will be provided online accounts to complete required surveys. Our centralized data collection center will not have access to randomization assignments in order to minimize bias in data collection. An outcomes assessment committee will blindly review all adverse event reports. Despite rigorous efforts to minimize missing data or outcome information, inevitably there will be some patients with missing outcome information. We will use the methods described above to mitigate biases due to missing data, or to assess the sensitivity of our results to assumptions about missing data.

### Data Management

At monthly intervals Statix, the central data collection agent, will transfer form files electronically to the Data Coordinating Center at the University of Maryland. The Data Coordinating Center will archive those form files, edit them for completeness of forms and data items, edit them for within-form and across-form logical consistency of data items, and report on the edits to the Clinical Coordinating Center at MUSC. Statix will work with the Data Coordinating Center and the Clinical Coordinating Center to achieve complete form submission and correct errors in data items submitted. Delinquent forms and data item corrections will be submitted through the Data Coordinating Center in a process of continual form file updating. The Data Coordinating Center will convert the form files into data analysis files. The biostatistician in the Data Coordinating Center at the University of Maryland, Baltimore, will analyze those data files in consultation with the Executive Oversight Committee for preparation of reports to the Data and Safety Monitoring Board (DSMB) every six months.

There will be no outcome or endpoint data exchange between clinical sites other than the sharing of enrollment figures and progress towards enrollment goals at each site. This information will be made available in a secure section of the clinical trial website that is password protected and available only to clinical sites and their staff.

### Reporting Plan

Publication and communication of our findings will be made in accordance with the CONSORT statement and its extension for pragmatic clinical trials. In addition to following the standard CONSORT guidelines, our reports will detail information about the characteristics of the study population and clinical centers so that providers and patients will have a good idea of the degree to which our findings can be generalized to their own populations. This will include information regarding clinical centers chosen, number of patients invited to participate, number participating, age and clinical conditions of patients (including comorbidities), patient adherence, and clinical management of patients beyond what is prescribed by treatment regimens (proportion receiving hip vs. knee operation types, anesthesia types, etc).

#### **3.1.4. Data Sharing**

Proposed dissemination activities are designed to achieve two objectives: (1) increasing of uptake findings of the study; and (2) integration of the shared decision on anticoagulation choice into routine care.

With regard to (1) presentations at scientific meetings and publications will target different clinical segments: orthopaedic surgeons, anticoagulation specialists, and hospitalists/general internists. Finding different variations on the themes of study results, we will deliberately present results at different national meetings, taking advantage of the diversity of investigators involved in the study. In addition, working with the Patient Advisory Board and the MUSC marketing department, we will create a dedicated PCORI PEPPER trial MUSC website to serve as a resource for patients and study sites as well as materials that advisory board members can post on patient advocacy organization websites

and can disseminate via social media. To reach health professionals that are not strong journal readers, we will create short descriptions of the study results for posting on the websites of participating institutions, on Medscape and Doximity medical social networks, and using LinkedIn groups and personal LinkedIn networks.

With regard to activity (2), we will perform additional analyses designed to help surgeons, physicians, and other medical providers apply the results to individual patients. We will examine associations between demographic factors and conjoint analysis studies, and describe this in publications where appropriate to help physicians tailor interpretations of the study. We will examine risks in subgroups to assess the degree to which non-inferiority of treatments extends to patients with different levels of risk factors (chronic illness, prior vascular disease, smoking, etc.) in order to provide guidance for tailoring stakeholder choice of intervention and balancing benefits and harms for specific individuals. Our purpose is not to assign causality but to develop models that, when exposed via the study website, can help providers and patients determine when there is truly non-inferiority. We will also adapt our preference elicitation tools into web friendly formats, coupled with explanations of the meaning elicitations, to help surgeons better understand what their patient values are and post these tools on publicly accessible web sites. All software systems developed for preference elicitation will be integrated into public web sites explaining methods, providing demonstrations, and that allow other investigators to adapt displays to improve explanations and/or integrate the displays with additional data. In addition, we will create a web site describing the results of the study, from a patient perspective based on input from our patient advisory board, that can serve as a prototype for subsequent developers of decision aids. We will integrate our tools into Epic electronic medical records (EMR) software (a widely used system among academic medical centers), using the Epic MyChart Portal and Patient Reported Outcomes toolkit available in the 2014 and 2015 release versions. We work to develop and pilot test appropriate workflows for integrating these Epic tools into routine care and make the software code available to other Epic sites.

### 3.1.5. Possible Limitations

The most predictable barriers to dissemination and implementation of possible findings that aspirin or warfarin are preferred to rivaroxaban would come from the pharmaceutical industry in light of the substantial investments and potential profits at stake with development of new anticoagulants. Uptake of such findings by patients, physicians, hospitals, and payers will be rapid in anticipation of safety advantages and cost savings.

Should rivaroxaban be found to be substantially superior in efficacy with comparable safety, uptake by patients and medical providers would be anticipated to be rapid based on effectiveness advantages and ease of administration. Surgical providers and hospitals/payers would be slower to adopt new approaches due to concern over relative safety as reflected by increased event rates for bleeding and higher drug and reoperation costs, respectively.

Conceptually, all principal barriers to dissemination have a common foundation: conversion of an area where surgeons have known what to do (e.g. most surgeons had a preferred post op anticoagulant and there were set business processes in place for routine care), to an area where they should practice shared decision making (SDM) and tailor choice of anticoagulant prophylaxis and practice to patients' preferences. Specific barriers will include:

- Acceptance of anticoagulation as an area where patients' preferences should determine therapy. Providers have to set aside their personal experiences and allow patients' preferences to contribute to treatment decisions;
- Cognitive biases. Changes in practices may result in physicians experiencing more memorable and dramatic events (deaths due to PE) than current practices (ie, availability bias);
- Differences in values between patients and physicians. Physicians often place a higher negative value on adverse events than disease related events, despite similar impacts on quality of life. Concerns about malpractice litigation may drive decision-making;
- Acceptance of the methods used to weigh the patient's risk-benefit perspective. Methodological questions about determination of balance between risk and benefit might prevent providers from adopting study results;
- Lack of tools for providers to accurately measure and learn about patients' preferences for anticoagulation in clinical settings. There are currently no good clinical tools to allow a provider to rapidly learn how a patient makes trade-offs between risks and benefits in anticoagulation. Thus it is difficult for providers to tailor care;
- Lack of tools for patients to support SDM on post arthroplasty anticoagulation. While there are several validated decision aids for patients to help decide whether to undergo joint replacement or elect anticoagulation (atrial fibrillation, for example) there are no joint replacement specific tools to elucidate anticoagulation choices, as informed by this study. It may then be difficult for patients to fully participate in anticoagulation decisions;

- Even if good tools are available, the complexity of trade-offs may prevent patients from fully participating in SDM. Patients with lower health literacy may not comprehend trade-off probabilities to share in decisions; and
- Lack of tools in electronic health records to aid in the incorporation of SDM into routine care. Currently there are not good tools to remind providers of SDM contexts in EHRs and to steer them toward SDM practices.

